### 11.6.2 Seizure Disorder

A summary of patients with a history of seizure disorders, the worsening of seizures or new onset seizures will be reported as AEs and the type, duration, and frequency of occurrence will be presented. Patients who experience worsening of their seizure disorder will be withdrawn from the study.

A summary table of seizure will be sorted by SOC and PT. All seizure data will be presented in a data listing.

### 11.6.3 Clinical Laboratory Evaluations

Laboratory parameters will be summarized for Double-Blind safety population and OLE safety population. Laboratory data (hematology, serum chemistry, and urinalysis) will be converted to the International System of Units (SI) units for reporting and processing purposes. Absolute values and changes from Baseline at each visit will be presented descriptively. Results reported as "<xx" or ">xx" will be imputed to "xx" for calculating the summary statistics.

Hematology, serum chemistry, and urinalysis will be summarized using descriptive statistics for numerical data and numbers and percentages for categorical data at each scheduled assessment. Numerical hematology, chemistry, and urinalysis results will be summarized using change from Baseline as well.

All clinical laboratory test results will be presented in data listings. Laboratory values that are outside of the normal reference range will be flagged in the data listings.

Urine drug screen will be listed only.

### 11.6.4 Vital Signs

Vital signs will include blood pressure, heart rate, respiratory rate, , and body temperature. Patients will be resting for at least 5 minutes before taking vital signs.

Vital signs results and corresponding change from study baseline values will be summarized at each visit using descriptive statistics by treatment group.

The reference ranges for the vitals are included in [Table 8](#) and will be used to categorize the assessments by Normal, High, or Low. The lowest and highest post-baseline results will be compared with that at the study baseline, and the "shifts" from study baseline will be summarized using the number and percentage of patients in each shift category by treatment group.

All vital signs measurements will be presented in a data listing; height will be presented within the demographic listing.

**Table 8: Vital Signs Reference Ranges**

Parameter	Low	High	Normal
Systolic Blood Pressure (mmHg)	< 80	> 130	80 - 130
Diastolic Blood Pressure (mmHg)	< 60	> 90	60 - 90
Heart Rate (beat per minutes)	< 60	> 100	60 - 100
Respiration Rate (breath per minutes)	< 12	> 20	12 - 20
Temperature (°C)	< 36.6	> 37.3	36.6 -- 37.3

### 11.6.5 Physical Examinations

Physical examination will include an evaluation of the head and neck as well as cardiovascular, respiratory, gastrointestinal, neurological, dermatological, and musculoskeletal systems (SoA for DBT phase and SoA for OLE phase in the protocol Amendment 5). Abbreviated physical examinations will be performed based on patient-reported symptoms (SoA for DBT phase and SoA for OLE phase in the protocol Amendment 5).

Physical examination data will be presented in a data listing.

### 11.6.6 12-Lead Electrocardiograms

Triplicate 12-lead ECGs will be obtained after the patient has been resting for at least 5 minutes. For clinically significant ECG findings, a follow-up ECG should be performed within 24 hours and again 7 days later to ensure that the abnormality is not worsening. Follow-up 12-lead ECGs may be performed locally and sent to the Investigator for assessment; the Investigator will submit all ECGs done locally to the central ECG vendor.

A core ECG laboratory will manage all ECG monitoring activities. All ECG results along with the investigator's interpretation, including the average of triplicate measurements at each timepoint, will be presented in data listings.

QT values will be presented with the implementation of corrections (i.e., Fridericia's) as defined in International Council for Harmonisation (ICH) Guidelines E14 by the following categories:

Absolute QT interval corrected for heart rate based on Fridericia's formula (QTcF) interval prolongation:

- QTcF interval <450 ms
- QTcF interval 450-480 ms
- QTcF interval 480-500 ms
- QTcF interval >500 ms

Change from baseline in QTcF interval:

- QTcF interval increases from baseline 30-60 ms
- QTcF interval increases from baseline >60 ms

In addition, potential QT prolongations will be categorized as:

- PR interval >300 msec
- QRS duration >140 msec
- PR interval increase from baseline >50%
- QRS duration increase from baseline >40%

- HR increase >65% from baseline
- HR decrease >40% from baseline

The actual values and change from baseline values at each time point will be summarized for the safety populations. The overall interpretation will also be summarized by timepoint as well as the worst post-baseline.

The average of the triplicates at each timepoint will be used in the summaries as defined in [Section 9.2](#).

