Patients with DM1 have an increased CV liability and risk of sudden death (Groh 2012). Cardiac manifestations of the disease present most commonly as arrhythmias or conduction disturbances (Lau et al 2015). Approximately 65% of patients have electrocardiogram (ECG) abnormalities, and specific ECG abnormalities have been noted as a sensitive predictor of sudden death, and thus may be useful for risk stratification in this population (Lau et al 2015; Sommerville et al 2017). Specifically, risk of sudden death is significantly elevated in patients whose ECG shows atrial arrhythmia, PR interval >240 msec, QRS duration >120 msec, or advanced atrioventricular block (AVB) (Groh 2012). Therefore, in this Phase 2 study, the exclusion criteria will ensure the enrollment of patients with minimal conduction defects and low risk for clinically significant cardiac arrhythmias. Because pitolisant has the potential for QT prolongation, patients with potential for QT prolongation are excluded, as are patients who are known cytochrome P450 (CYP) 2D6 poor metabolizers (PMs) (pitolisant exposure is 2- to 3-fold higher in CYP2D6 PMs). In addition, patients' CV status will be monitored clinically throughout the study using triplicate ECG assessments and Holter monitoring. This additional monitoring is warranted because up to 32% of patients with DM1 with a normal ECG may have arrhythmias and conduction abnormalities that are only detectable using arrhythmia monitoring (Merlevede et al 2002).

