- 11. Has a diagnosis of moderate or severe renal impairment (eGFR ≥15 to ≤59 mL/minute/1.73 m^2) or moderate hepatic impairment (Child-Pugh B) at Screening or during the Double-Blind Treatment Phase.
- 12. Has a family history of sudden cardiac death, unexplained death, or death from a primary dysrhythmia potentially associated with QT prolongation in any family member (i.e., first degree relative such as parent, sibling, or offspring).
- 13. Has a history of unexplained syncope.
- 14. Has a history of long corrected QT interval (QTc) syndrome or corrected QT interval using Fridericia's formula (QTcF) >450 msec for males or >470 msec for females (QTcF = QT /  $3\sqrt{RR}$ ) sustained atrial fibrillation (AF) or left ventricular ejection fraction <50%.

- 15. Has a history of documented symptomatic arrhythmias (e.g., ECG, Holter monitor).
- 16. Electrocardiogram abnormalities during a 10-second, 12-lead ECG at Screening of first degree AVB (PR interval >220 msec), QRS >120 msec, heart rate (HR) <50 beats per minute (bpm), marked T-wave abnormalities, more than single atrial premature complexes (APCs) or premature ventricular contractions (PVCs), left bundle branch block, or Brugada pattern type 1.

Note: Patients with  $1^{st}$  degree AVB with a PR interval  $\geq$  220 msec, who are treated prophylactically with an allowable implanted device are not excluded from the study.

- 17. Based on Holter monitor, any episode of 3rd degree AVB, any prolonged episode of second degree AVB (>2 episodes during waking hours, >6 episodes during sleep), any prolonged episode of 2nd degree AVB (>10 seconds), any asystole longer than 3.5 seconds, any run of ventricular tachycardia (VT) >6 beats, frequent runs of non-sustained VT (>5/24 hour), >400 PVCs/24 hours, AF or paroxysmal AF, or frequent or complex atrial arrhythmias.
- 18. Has history of New York Heart Association (NYHA) class III or class IV heart failure.
- 19. Has an implanted defibrillator or implanted biventricular pacemaker.

Note: Patients with implanted univentricular pacemakers that are used prophylactically to prevent or treat bradycardia or heart block may be included.

- 20. Is receiving a medication known to prolong the QT interval.
- 21. Has a history of clinically significant hypokalemia or hypomagnesemia that cannot be adequately controlled by supplementation.

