### 6.3.4.2. 12-Lead Electrocardiograms

Triplicate 12-lead ECGs will be obtained for all patients at every on-site study visit as detailed in Section 7. Patients should be resting for at least 5 minutes before each 12-lead ECG is performed. At Visit 3 and Visit 5, triplicate 12-lead ECGs will be performed with every blood sample collected for PK analyses, as detailed in Section 7.2.4.1 and Section 7.2.4.4, respectively. The ECGs should be done prior to and within 15 minutes of the blood draw for PK analyses.

For clinically significant ECG findings, a follow-up ECG should be performed within 24 hours and again 7 days later to ensure the abnormality is not worsening. Follow-up 12-lead ECGs may be performed locally and sent to the Investigator for assessment; the Investigator will submit all ECGs done locally to the central ECG vendor.

The following ECG abnormalities should be promptly addressed by the Investigator and will require discontinuation of study drug (Section 4.4.1):

• Any ECG finding that demonstrates QT prolongation (i.e., QTcF >500 msec or an increase >60 msec) regardless of resultant QTc value

In addition to a potential QT prolongation, the Medical Monitor should be consulted for:

- PR interval >300 msec, QRS duration >140 msec, or any increase from baseline in PR or QRS greater than 50% or 40%, respectively
- HR increase >65% over baseline or decrease >40% compared with baseline

In the event of these clinically significant abnormal PR interval, QRS duration, or HR ECG results, the ECG should be repeated as soon as possible and if done the next day, attempts should be made to perform the repeat ECG at the same time of day that the abnormal ECG was obtained. If the event persists or worsens, study drug may be interrupted for 2 to 3 days and the ECG will be repeated on the third day. If the abnormality has improved, study drug dosing may resume. If the condition persists or worsens after the study drug interruption, the Investigator, in consultation with the Medical Monitor, will decide whether treatment should be permanently discontinued.

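### SAP 11.6.6 counts PR, QRS and heart-rate outliers only at the Medical Monitor consultation triggers, so many new crossings of PR 240 ms, QRS 120 ms or HR 50 bpm fall in no numeric ECG category

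*SAP*

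**What the plan says.** Apart from the QTcF bands, SAP 11.6.6 lists six numeric ECG categories. Two are absolute: "PR interval >300 msec" and "QRS duration >140 msec". Four are relative to baseline: "PR interval increase from baseline >50" and "QRS duration increase from baseline >40" (both in per cent), a heart-rate rise above 65%, and "HR decrease >40% from baseline". Heart rate has no absolute floor.

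These are the Medical Monitor consultation triggers of Protocol 6.3.4.2, which names "PR interval >300 msec, QRS duration >140 msec, or any increase from baseline in PR or QRS greater than 50% or 40%, respectively" and the same two heart-rate changes.

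The protocol gives lower figures in two other places:

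- Section 1.2 says that the risk of sudden death in DM1 is significantly raised with atrial arrhythmia, "PR interval >240 msec, QRS duration >120 msec, or advanced atrioventricular block (AVB").
- Exclusion 16 in Section 4.1.2 bars, at Screening, PR above 220 ms (unless treated prophylactically with an allowed implanted device) and "QRS >120 msec, heart rate (HR) <50 beats per minute (bpm").

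No PR, QRS or heart-rate category in SAP 11.6.6 sits at any of these figures.

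**The concern.** A consultation trigger tells a site when to call the Medical Monitor. An outlier category tells the reader of the report how many patients per arm moved into a range of interest. The SAP uses one set of numbers for both purposes. For QTcF the same section is graded from 450 ms, which is the entry limit for males, but conduction and rate have no comparable lower band.

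The primary objective covers safety as well as efficacy, and Protocol 6.3.4 says that the later ECGs are meant to detect changes in cardiovascular parameters. With about 30 patients randomized 1:1:1, an arm has about 10, so one uncounted patient is about 10 percentage points of that arm's rate. The by-arm PR, QRS and heart-rate rows could all read zero although a patient had newly passed a figure that the protocol links to sudden death or used to bar entry.

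**Working it through.** The plan gives no figure to reproduce. The check applies the SAP rule (absolute or relative criterion met) to a patient who starts within a limit and then crosses it.

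**Inputs.** Category cut-offs: SAP 11.6.6. Risk figures PR 240 and QRS 120: Protocol 1.2. Entry limits PR 220, QRS 120 and HR 50: Exclusion 16. The baseline values below are illustrations.

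**Step 1: break-even baselines.** The relative rule alone catches every crossing when the limit itself already reaches the relative change:

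- PR: 240 / 1.5 = 160 ms. Every crossing from a baseline of 160 or lower is counted.
- QRS: 120 / 1.4 = 85.7 ms. Every crossing from a baseline of 85.7 or lower is counted.
- HR: 50 / (1 - 0.40) = 83.3 bpm. Every crossing from a baseline of 83.3 or higher is counted.

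**Step 2: edges in whole units.** The smallest possible crossing is tested on each side of the edge:

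- PR 160 to 241: 241/160 = 1.506, counted. PR 161 to 241: 241/161 = 1.497, not counted.
- QRS 86 to 121: 121/86 = 1.407, counted. QRS 87 to 121: 121/87 = 1.391, not counted.
- HR 82 to 49: 1 - 49/82 = 40.2%, counted. HR 81 to 49: 1 - 49/81 = 39.5%, not counted.

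Some crossings are therefore missed from baseline PR 161-220, QRS 87-120 and HR 50-81. The outer ends (220, 120, 50) are the entry limits. A device-treated patient may start above PR 220.

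**Step 3: width of the uncounted range.**

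| Measure | Baseline | Uncounted values after crossing | Reason |
|---|---|---|---|
| PR (ms) | 180 | 241-270 | 180 x 1.5 = 270 |
| PR (ms) | 200-220 | 241-300 (all) | 200 x 1.5 = 300, so the relative rule adds nothing below 300 |
| QRS (ms) | 90 | 121-126 | 90 x 1.4 = 126 |
| QRS (ms) | 100-120 | 121-140 (all) | 100 x 1.4 = 140 |
| HR (bpm) | 60 | 36-49 | 60 x 0.6 = 36 |
| HR (bpm) | 70 | 42-49 | 70 x 0.6 = 42 |
| HR (bpm) | 80 | 48-49 | 80 x 0.6 = 48 |

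**Step 4: examples.** PR 200 to 295 is +47.5% and below 300. QRS 100 to 138 is +38% and below 140. ECG heart rate 70 to 44 is -37.1%. None meets a numeric ECG category. By contrast, PR 150 to 241 (+60.7%), QRS 85 to 121 (+42.4%) and HR 90 to 49 (-45.6%) are all counted.

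The gap is wide for PR and QRS baselines close to the entry limits. It narrows to nothing at PR 160, at QRS just above 85 and at HR just above 81.

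**The case against.** **The SAP follows the protocol.** Its categories match the consultation triggers, and Protocol 9.4.3 promises counts of ECG abnormalities without naming limits. A reader might infer that SAP and protocol contradict each other. They do not: Section 1.2 is background risk stratification, Exclusion 16 applies at entry, and neither defines an on-treatment outlier. Nor does any passage link heart rate below 50 to sudden death; it is an entry limit only. This objection stands in full.

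**The relative rules catch some crossings.** A reader might infer that everyone who crosses the protocol's figures is missed. The working shows otherwise: the +50%, +40% and -40% rules count every crossing from lower PR and QRS baselines and from higher heart rates. This also stands.

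**Other outputs show such patients.** A reader might infer that they would vanish from the report. They would not:

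- SAP 11.6.6 summarizes actual values and changes at each timepoint, and SAP 11 includes the minimum and maximum. A visit-level mean PR of 295 would be reflected in the maximum.
- The overall ECG interpretation is summarized by timepoint and at its worst after baseline, using the worst reading of the triplicate (SAP 9.2.2).
- All ECG results are listed, and Holter abnormalities are counted (SAP 11.6.7).
- Clinically significant ECG findings are recorded as adverse events (Protocol 6.3.1).
- If it was also seen in vital signs, a heart rate going from 70 to 44 is a Normal-to-Low shift (SAP 11.6.4, Table 8).

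This stands as partial visibility. A maximum shows one value and does not say how many patients crossed or whether the crossing was new. The overall interpretation and adverse-event recording rest on judgement. Table 8 codes everything below 60 bpm as Low, so 55 to 44 shows as Low to Low, and it does not cover PR or QRS. None of these outputs counts new crossings by arm.

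**Conclusion.** The point holds as a sensitivity gap in descriptive safety tables. Patients who newly cross PR 240, QRS 120 or HR 50 are not counted in any numeric ECG category of SAP 11.6.6 unless they also meet the larger absolute or relative criteria. For PR baselines of 200-220 ms, every value from 241 to 300 is uncounted. For QRS baselines of 100-120 ms, every value from 121 to 140 is uncounted. For heart rate the range depends on the baseline and shrinks to 48-49 bpm at a baseline of 80.

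The ranges assume whole-unit values and baselines within the entry limits. How many patients would be affected cannot be stated, because the documents give no baseline ECG distribution.

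A reader might also infer that the consultation triggers themselves are set wrongly. The documents do not support that: a trigger for consultation and a background risk figure can differ without contradiction, and this point takes no position on clinical management.

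The addition is worth making. Safety is part of the primary objective, the figures are the protocol's own, and the cost is small. The study is exploratory and no formal safety statistics are planned, so the rows would be descriptive only.

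**What to change.** Before unblinding, add to SAP 11.6.6 descriptive counts and percentages, by treatment arm, of patients with a post-baseline value beyond each limit who were not beyond it at Baseline:

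- PR above 240 ms
- QRS above 120 ms
- heart rate below 50 bpm

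Show device-treated patients separately, since Exclusion 16 lets them enter with a longer PR. Keep the six existing categories. State in the table note that the new rows are reporting categories only, that PR 240 and QRS 120 come from Protocol 1.2 and HR 50 from Exclusion 16 (the PR entry limit is 220), and that the triggers in Protocol 6.3.4.2 are unchanged.

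The cost is three more table rows from ECG data already collected. The downside is a few more incidental outlier counts in arms of about 10, where a single patient moves the percentage by about 10 points. The counts should therefore be read beside the listings.

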### **11.6.7 Holter Monitoring**

Patients will be fitted with a Holter monitor, which they will wear for 24 hours before returning the device and for all abnormal Holter monitor findings considered clinically significant by the Investigator, additional evaluation, including an unscheduled ECG, is required.

A core ECG laboratory will manage all Holter monitoring activities. All Holter results will be presented in data listings.

The actual values and change from baseline values at each time point will be summarized for the safety populations. Abnormalities will be summarized by frequency count and percentages.

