### 6.3.4. Holter Monitoring and 12-Lead Electrocardiograms

Holter monitoring and triplicate 12-lead ECGs will be performed at Screening and during the Double-Blind Treatment Phase and OLE Phase of the study as detailed in Section 7. The Holter monitoring performed at Screening and the ECGs performed at Screening and Baseline will determine whether an exclusionary CV issue is present, and assessment at later time points during the study is designed to detect any changes in CV parameters and to detect the development of arrhythmias.

A core ECG laboratory will manage all ECG and Holter monitoring activities, including standardization and training of the technical staff at all study sites in proper electrode placement, operation of the hardware, and management of patients during testing. Electrocardiogram and Holter monitoring data will be transmitted electronically to the core laboratory and will be promptly interpreted by trained cardiologists. Pre-specified criteria for QT, QRS duration, AVB, and arrhythmias will trigger immediate notifications.

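### The SAP plans no Baseline shift table or new-onset count for categorical Holter abnormalities or the ECG overall interpretation, so persisting and new findings are counted together

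*SAP*

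**What the plan says.** Protocol 6.3.4 gives the purpose of the recordings after entry: "assessment at later time points during the study is designed to detect any changes in CV parameters and to detect the development of arrhythmias". A 24-hour Holter is scheduled at Screening, at Visit 3 (Day 22) and, in the open-label extension (OLE), at Visit 6 (Day 99). Triplicate ECGs are taken at every on-site visit.

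The SAP then plans these summaries:

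- **Holter, numeric (11.6.7):** "The actual values and change from baseline values at each time point will be summarized for the safety populations".
- **Holter, categorical (11.6.7):** "Abnormalities will be summarized by frequency count and percentages". Nothing is said about Baseline status, new onset or a shift format.
- **Holter, patient level (11.6.7):** "All Holter results will be presented in data listings".
- **ECG overall interpretation (11.6.6):** "The overall interpretation will also be summarized by timepoint as well as the worst post-baseline". No pairing with the Baseline interpretation is specified.
- **ECG intervals and rate (11.6.6):** some categories are defined as change from Baseline, for example "QTcF interval increases from baseline >60 ms".
- **Vital signs (11.6.4):** the lowest and highest post-baseline results are compared with Baseline, and shifts "from study baseline will be summarized using the number and percentage of patients in each shift category by treatment group".

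Protocol 9.4.3 also promises only counts and percentages for ECG and Holter abnormalities, so it does not fill the gap.

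**The concern.** The development of an arrhythmia is a within-patient transition: absent before drug, present after. A count of abnormal patients measures prevalence. A patient with the same minor rhythm finding at Screening and at Day 22 adds one to the table, and so does a patient whose finding first appears at Day 22. The worst post-baseline ECG interpretation has the same property. It also takes the worst of several visits and sets it beside no paired Baseline category.

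Cardiac rhythm is a central safety question here. Protocol 1.4 states that the drug prolongs QT, and Protocol 1.2 justifies the added monitoring on the ground that "up to 32% of patients with DM1 with a normal ECG may have arrhythmias and conduction abnormalities that are only detectable using arrhythmia monitoring". In the Double-Blind Phase the placebo arm gives some protection, because background findings are expected equally in all arms. The OLE has no concurrent control, so a bare count at Day 99 has nothing to be read against. The SAP uses Baseline shift tables for vital signs, ESS, CGI-S and PGI-S, but not for these two cardiac outputs.

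**Working it through.** The plan states no figure on this point, so there is nothing to reproduce. The check compares the planned outputs, asks what marginal counts can show, and gives an illustration of size.

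**1. Which outputs refer to Baseline**

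| Output | Refers to the patient's Baseline? |
|---|---|
| Numeric Holter and ECG values | Yes, change from Baseline |
| QTcF increase 30-60 ms and >60 ms; PR increase >50%; QRS increase >40%; HR increase >65%; HR decrease >40% | Yes, six categories |
| Clinically significant Holter or ECG findings | Yes, through adverse events (Protocol 6.3.1) and the new-onset-or-worsening rule (SAP 11.6.1) |
| Holter abnormality counts | No |
| ECG overall interpretation, by timepoint and worst post-baseline | No within-patient pairing |

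**2. Whether the data for a pairing exist.** They do. SAP 9.3 defines Baseline as the last non-missing pre-dose record and uses it for both phases, so the Screening Holter normally serves. SAP 9.2.2 takes the worst interpretation across the triplicate and applies the selection rules to Baseline as well as to later visits. The Baseline ECG category is therefore already derived; only the cross-tabulation is missing.

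**3. What marginal counts can show.** With b of n patients abnormal at Baseline and v of n abnormal later, the number of new cases can lie anywhere from max(0, v − b) to min(v, n − b). Take n = 10, b = 3, v = 3:

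- lower bound: max(0, 3 − 3) = 0
- upper bound: min(3, 10 − 3) = 3

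Even with the Baseline count printed alongside, 3/10 and 3/10 fits no new case or three.

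**4. Illustration of size, on assumed rates.** Inputs: about 30 patients randomized 1:1:1 (SAP 8.1), so about 10 per arm and 20 on active drug. The documents give no abnormality rate after the entry exclusions. I assume a rate p at entry of 5% to 32%; the upper end is the Protocol 1.2 figure, which applies before this trial's exclusions.

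- Expected patients entering with an abnormality: 10p = 0.5 to 3.2 per arm; 20p = 1.0 to 6.4 on active drug; 30p = 1.5 to 9.6 if all 30 enter the OLE.
- Chance of at least one such patient in an arm of 10: 1 − (1 − p)^10 = 1 − 0.95^10 = 40% at p = 5%, and 1 − 0.68^10 = 98% at p = 32%.
- Suppose entry findings persist and an assumed q = 10% of the remaining patients develop a new one. The share of the on-treatment count that is new is (1 − p)q / [p + (1 − p)q]. At p = 5% this is 0.095/0.145 = 66%. At p = 32% it is 0.068/0.388 = 18%.

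Depending on the entry rate, the same table could consist mostly of new findings or mostly of old ones, and it would not show which.

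**The case against.** The strongest reply is that Baseline is far from absent. Numeric results and six interval or rate categories are measured against it, including the QTcF increases that bear directly on the drug's stated effect. In a trial of about 30 patients, all Holter and ECG results are listed and anyone can compare Screening with Day 22. Findings judged clinically significant must be recorded as adverse events and are then tabulated as treatment-emergent only if new or worsened. Exclusion criteria 14 to 17 remove the major rhythm and conduction abnormalities, and the Double-Blind Phase has a randomized placebo arm. SAP 11.6.7 is also a single general sentence, and the table shells are not public.

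Most of this stands, and it rules out several stronger readings:

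- A reader might infer that new arrhythmias cannot be identified at all. The Screening Holter, the listings and the adverse event route show otherwise. They are simply not separated in any planned table of these categorical results.
- A reader might infer that pre-existing findings will be presented as effects of the drug. The SAP does not label these counts treatment-emergent or on-drug.
- A reader might take the 65% of DM1 patients with ECG abnormalities in Protocol 1.2 as the rate to expect here. That figure describes DM1 patients generally, and criterion 16 excludes many such ECGs.
- A reader might want a false-signal probability. With 10 per arm and no drug effect, the chance that the higher-dose arm shows at least two more abnormal patients than placebo is 12% at a 10% background and 24% at 32%. The same formula also gives 12% for new findings if their rate were 10%. The documents supply no rate, and no decision turns on two patients, so this does not size the problem.

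Three things are left. The interval categories do not cover rhythm findings. The adverse event route misses abnormalities not judged clinically significant, and the exclusion thresholds still let lesser findings in (for example, up to 400 premature ventricular contractions in 24 hours). Listings permit reconstruction by hand but are not a pre-specified summary.

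**Conclusion.** The point holds as a gap in table specification. No planned summary separates new from persisting findings for categorical Holter abnormalities or for the ECG overall interpretation, although the protocol gives the development of arrhythmias as a reason for the later recordings. The practical effect is confined to findings not reported as adverse events, and it is greatest for the Day 99 Holter in the OLE, where there is no concurrent control.

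That conclusion rests on the wording of SAP 11.6.6, 11.6.7 and Protocol 9.4.3 and needs no numerical assumption. The size does: 0.5 to 3.2 patients per arm carrying an abnormality into the trial depends on an assumed entry rate of 5% to 32%, and exclusions may put the true rate toward the lower part of that range. A reader might go further and conclude that cardiac safety cannot be assessed from this trial. The documents do not support that, given the Baseline-referenced interval categories, the listings and the adverse event tables. This is an inexpensive improvement in reporting.

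**What to change.** Keep the existing counts and add the following.

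- **SAP 11.6.7, new-onset count:** for each abnormality type, the number and percentage of patients with it at Day 22 (by arm) and at Day 99 (OLE), with the denominator restricted to patients without that abnormality at Baseline, meaning the last pre-dose Holter.
- **SAP 11.6.7, shift table:** Baseline normal or abnormal against post-baseline normal or abnormal, at the same two timepoints. The per-type count is needed as well, because a patient with one abnormality at Screening and a different one at Day 22 would appear here only as abnormal to abnormal.
- **SAP 11.6.6:** cross-tabulate the Baseline overall interpretation against the worst post-baseline interpretation, in the shift format SAP 11.6.4 already specifies for vital signs.

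The cost is a few sentences of SAP text and a few table shells. The Screening Holter and Baseline ECG are already collected and Baseline is already defined, so no new data are needed and no clinical procedure changes.
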